#### **2.3.1.2 *Per-protocol population***

The per-protocol (PP) population is a subset of the mITT population excluding patients with any major protocol deviations that have significant impact on the primary study objective, analyzed according to the treatment actually received.

Major protocol deviations that do not cause exclusion from mITT population, but have significant impact on the primary study objective are as follows:

- Poor adherence to the study protocol
- IVUS not performed from Week 34 to Week 38 during efficacy treatment period, which is defined as the time from the day of randomization to the last study treatment administration + 21 days.
- Patients with analyzed vessel length less than 10 mm.
- Patients who do not meet the following inclusion criteria.
  - Patient hospitalized for any ACS
  - LDL-C at patient selection (either Friedewald method or direct methods measured at each study site)  $\geq 100$  mg/dL for patients enrolled based on the protocol amendment 1;  $\geq 70$  mg/dL for patients enrolled based on the protocol amendment 2 or later.
  - Patient who undergoes IVUS imaging with at least  $>50\%$  stenosis angiographically within 1 week after the ACS onset. The IVUS imaging should be performed in the culprit vessels with some levels of atherosclerosis/stenosis.
  - Patients aged  $\geq 20$  years old at ACS diagnosis.
- Patients who meet the following exclusion criteria.
  - Patient who has been previously treated with at least one dose of any anti-PCSK9 monoclonal antibody.
  - Patient on LDL apheresis

- Patient who has withdrawn consent before enrolment/randomization (starting from signed informed consent form).

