6 STUDY DESIGN

This is a phase 4, open-label, 1:1 randomized, blinded IVUS analysis, parallel group, multicenter study to investigate the effect of alirocumab on coronary atheroma volume in Japanese patients with hypercholesterolemia, who have recently suffered from ACS and are failing to reach the recommended LDL-C levels as defined by JAS guidelines for very high CV disease risk in spite of stable statin therapy. Randomization will be stratified by 'on statin therapy' or 'not on statin' therapy at the time of ACS onset. As a phase 4 study, the dose regimen is in line with the approved regimen in Japan; starting dose is 75 mg Q2W with up-titration to 150 mg Q2W if patients do not reach their target LDL-C level.

Approximately 200 patients from approximately 40 study sites will be enrolled and randomized with a treatment period of 9 months. Patients who suffer ACS events despite stable statin therapy and whose LDL-C is ≥ 100 mg/dL will be enrolled. If patients are not on any statin therapy at the time of ACS onset, they will start either atorvastatin 10 mg/day or rosuvastatin 5 mg/day immediately after the ACS diagnosis, and the patients whose LDL-C is not adequately controlled with statin (in principle, LDL-C target level ≥ 100 mg/dL, but this may not apply if the responsible physician considers LDL-C level inadequate on statin. Patients who have LDL-C < 70 mg/dL cannot be enrolled) at 2 to 4 weeks after the ACS diagnosis will be also enrolled.

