7 SELECTION OF PATIENTS

7.1 INCLUSION CRITERIA

I 01. Patients hospitalized for ACS (ST-elevation myocardial infarction [STEMI], non ST-elevation myocardial infarction [NSTEMI], unstable angina)

Definition of ACS:

A) ST-elevation myocardial infarction (STEMI)

Patients meet all of the following items:

1. A chest symptom (chest pain, shortness of breath, etc.) suggestive of ischemia.
2. At least 1 mm of ST elevation in two or more consecutive chest leads or limb leads on ECG or a new left bundle branch block.
3. An elevation in blood test value (positive troponin T or troponin I, or creatine phosphokinase (CPK) ≥ 2 times the upper limit of normal) suggestive of myocardial necrosis.

B) Non-ST-elevation myocardial infarction (NSTEMI)

Patients meet all of the following items:

1. A chest symptom (chest pain, shortness of breath, etc.) suggestive of ischemia.
2. ST depression >0.5 mm, negative T-wave (≥ 3 mm: dynamic T-wave inversion), or transient ST elevation ≤ 0.5 mm.
3. An elevation in blood test value (positive troponin T or troponin I, or CPK ≥ 2 times the upper limit of normal) suggestive of myocardial necrosis.

C) Unstable angina

The definition of unstable angina pectoris requires '1' and either of items '2 - 6' described below:

1. A chest symptom (chest pain, shortness of breath, etc.) suggestive of ischemia.
2. ST depression ≥ 0.5 mm or T-wave negative conversion ≥ 3 mm.
3. An elevation in troponin T.
4. Confirmation of the coronary lesion responsible for acute coronary syndrome by diagnostic imaging (coronary angiography, multiple detector computed tomography, etc.).
5. New decrease in wall motion by echocardiogram.
6. Reversible decrease in myocardial blood perfusion induced by drug, exercise, or thallium scintigraphy.

I 02. LDL-C ≥ 100 mg/dL at ACS diagnosis (either by Friedewald method or direct methods measured at each study site):

- Patients who have already been on any statin therapy at ACS onset. If the statin is not atorvastatin or rosuvastatin, statin will be changed to either atorvastatin ≥ 10 mg/day or rosuvastatin ≥ 5 mg/day immediately after the ACS diagnosis based on Investigators' medical judgment.

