- If patients have not been on any statin therapy at ACS onset, either atorvastatin 10 mg/day or rosuvastatin 5 mg/day is started immediately after the ACS diagnosis, and LDL-C is not adequately controlled with statin at 2 to 4 weeks after the ACS diagnosis (in principle, LDL-C target level ≥ 100 mg/dL, but this may not apply if the responsible physician considers the LDL-C level inadequate on statin. Patients who have LDL-C < 70 mg/dL cannot be enrolled).

I 03. Patients who has stenosis of at least $>50\%$ on coronary angiography within 1 week after the ACS onset, and has analyzable coronary IVUS image. The evaluated segment of IVUS is a segment where a physician considers the IVUS imaging is possible (regardless of culprit vessels or not culprit vessels) other than the culprit lesions.

I 04. Patients aged ≥ 20 years old at ACS diagnosis.

I 05. Patients who meet any of the following conditions.

- Negative hepatitis B virus surface antigen, negative total hepatitis B virus core antibody, and negative hepatitis C virus antibody.
- Negative hepatitis B virus surface antigen, positive total hepatitis B virus core antibody, negative hepatitis B virus DNA and negative hepatitis C virus antibody.

I 06. Written informed consent.

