## 1.6 STATISTICAL MODIFICATIONS MADE IN THE STATISTICAL ANALYSIS PLAN

The SAP version 1 was modified between the study start and database lock (DBL) for the main study in order to follow the last amended protocol, to address the further information on IVUS and optical coherence tomography (OCT) imaging analysis, to keep a consistency with the study objectives, and to correct erroneous descriptions. The changes in the SAP from version 1 to version 2 are as follows:

- **Section 2.3.1:** In the definition of mITT population, "Another one assessed during the efficacy treatment period and within the Week 36 analysis window", which is mentioned in the 3rd item of [Table 1](#) in [Section 1.7](#), was changed to "Another one assessed after 24 weeks of treatment ", since the statement in version 1 was inconsistent with the last amended protocol, and IVUS imaging outside the efficacy treatment period could not be considered as protocol deviation.
- **Section 2.3.1.1:** In the definition of PP population, the following criteria were changed:
  - "Patients with analyzed vessel length less than 10 mm" was added, since it is considered major deviation from IVUS imaging procedure and it may have an impact on IVUS parameters.
  - "LDL-C  $\geq$ 100 mg/dL" was changed to "LDL-C at patient selection  $\geq$ 100 mg/dL for patients enrolled based on the protocol amendment 1;  $\geq$ 70 mg/dL for patients enrolled based on the protocol amendment 2 or later" according to the amended protocol.
  - "Background therapy deviation" was removed, since the study team found that in the study protocol the use of background therapy including statin is eventually dependent upon the doctor and so deviation related to background therapy cannot be specified.
- Several analyses including substudy analyses for optical coherence tomography (OCT), additional efficacy analyses (Section 2.4.4.4) were removed, since they are beyond the study objectives.

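### The per-protocol LDL-C cut-off of ≥70 mg/dL for everyone enrolled under amendment 2 or later does not match I 02, which keeps ≥100 mg/dL for patients on a statin at ACS onset

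*SAP*

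**What the plan says.** **Protocol.** I 02 in Section 7.1 is headed by "LDL-C ≥ 100 mg/dL at ACS diagnosis (either by Friedewald method or direct methods measured at each study site". Two branches sit under that heading.

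- The first covers "Patients who have already been on any statin therapy at ACS onset". It adds an instruction about the type of statin but gives no lower LDL-C level.
- The second covers patients not on a statin at onset. They start one, and must then show that "LDL-C is not adequately controlled with statin at 2 to 4 weeks after the ACS diagnosis". The level is in principle still ≥100 mg/dL, but "this may not apply if the responsible physician considers the LDL-C level inadequate on statin". There is a floor: "Patients who have LDL-C < 70 mg/dL cannot be enrolled".

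The synopsis repeats I 02 with the same structure. Section 6 says of the first group: "Patients who suffer ACS events despite stable statin therapy and whose LDL-C is ≥ 100 mg/dL will be enrolled". The design rationale in Section 4 says the same.

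**SAP.** Section 1.1 mentions the 70 mg/dL floor only in its bullet for patients not on a statin at onset. Section 2.3.1.2 lists the inclusion criteria whose breach removes a patient from PP. There, LDL-C at patient selection must be ≥100 mg/dL under amendment 1 and ≥70 "mg/dL for patients enrolled based on the protocol amendment 2 or later". The rule is not split by statin status. Section 1.6 explains that it was changed in SAP version 2 "according to the amended protocol".

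The PP set supports the primary endpoint (SAP 2.4.4.1, supportive analyses) and the IVUS secondary endpoints (SAP 2.4.4.2).

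**The concern.** The SAP presents this bullet as a restatement of an inclusion criterion. It has taken a floor that the protocol gives to one randomization stratum, for one later measurement, and applied it to both strata. The protocol supplied is amendment 3, so it falls under the SAP's second limb, and it still asks for ≥100 mg/dL in the on-statin stratum.

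At stake is whether the PP set does its job for this criterion. The SAP itself counts entry LDL-C among the few eligibility items that matter for the primary objective. A PP rule that passes patients who break the item cannot show what those breaches do to the result.

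**Working it through.** No figure in the plan is in dispute, so the check is to apply both rules to the possible LDL-C values of a patient enrolled under amendment 2 or later.

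| Patient | I 02 (Protocol 7.1) | PP rule (SAP 2.3.1.2) | Result |
|---|---|---|---|
| (a) On statin at onset, 70–99 mg/dL at ACS diagnosis | Fails | Passes | **Mismatch** |
| (b) Not on statin, ≥100 at diagnosis, 70–99 at 2 to 4 weeks | Eligible if the physician judges control inadequate | Passes | Agree |
| (c) Not on statin, <100 at diagnosis, ≥70 at 2 to 4 weeks | Fails only if the heading binds this branch | Passes if the later value is used | Unresolved in the protocol |
| (d) <70 mg/dL at selection, either branch | Fails | Fails | Agree |

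Case (a) is clear. I 02, Section 4 and Section 6 all give ≥100 mg/dL, and no passage gives this group a lower level. For these patients the only LDL-C that I 02 names is the one at ACS diagnosis.

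Case (b) shows that the 70 mg/dL figure is right for the group it was written for, provided the 2-to-4-week value is the one tested.

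Case (c) turns on the protocol. The I 02 heading stands above both branches, but Sections 4 and 6 describe entry of patients not on a statin by the 2-to-4-week value alone.

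**Which measurement.** SAP 2.1.1 ties LDL-C at patient selection to a case report form page, and a footnote to the flow chart in Protocol 1.2 describes it as the value used for eligibility. For patients not on a statin, I 02 can involve two values, and the SAP does not say which is tested. If the diagnosis value were used, the 70 mg/dL floor at 2 to 4 weeks would go unchecked.

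**Scale, for illustration only.** The documents give no count in case (a). The planned evaluable number is 150 of 200 (Protocol 11.1), and this reproduces: 150 / (1 − 0.25) = 200, and 75 per arm gives 90.06% t-test power for a difference of 8 with SD 15. *Assume* that 30–50% are on a statin at onset and that 3–10% of those were entered at 70–99 mg/dL:

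- low: 150 × 0.30 × 0.03 = 1.35 patients
- high: 150 × 0.50 × 0.10 = 7.5 patients

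Zero is also possible, and the base would shrink once amendment 1 enrolees and other PP exclusions come off. At the high end, suppose those patients are balanced between arms and have no treatment effect while all others have the planned 8 points. The PP difference is then (1 − 7.5/150) × 8 = 0.95 × 8 = 7.6, a shift of 0.4. The planned standard error of the difference is 15 × √(2/75) = 2.45, so the shift is 0.4 / 2.45 = 0.16 standard errors.

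**The case against.** The best defence is that the rule may never matter. At the randomization visit (Protocol 10.1.1.1) the registration center makes a final check of eligibility before it communicates the arm, so an on-statin patient at 70–99 mg/dL would have to get past that check. This stands as to the count. A reader might infer that the PP set does contain ineligible patients; the documents do not show that any were enrolled. But the PP criterion exists to catch breaches that get past the check, and for this group it would not.

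A second defence is that such patients would be visible elsewhere. SAP 2.1.1 tabulates selection LDL-C in bands that include 70–80 and 80–100 mg/dL, SAP 2.4.1 repeats the baseline tables by randomization stratum, and SAP 2.2 summarises major deviations by arm. This also stands, but it does not correct the PP set. The subgroup analyses by baseline LDL-C help less, because they use the last central-laboratory value up to randomization. The PP exclusion for poor adherence to the protocol is undefined and cannot be relied on to remove these patients.

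Two stronger readings are tempting.

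- A reader might infer that agreement between PP and mITT is partly built in. That does not follow. PP also differs by the Week 34–38 IVUS window, analyzed vessel length, adherence, other eligibility items and analysis by treatment received.
- A reader might infer that the SAP also wrongly drops ≥100 mg/dL at diagnosis for patients not on a statin. The I 02 heading can be read that way, but Protocol Sections 4 and 6 and SAP 1.1 state no such test for that group. This is an ambiguity in the protocol, not a proven SAP error.

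Finally, the sponsor may have meant 70 mg/dL for both strata. The protocol text would then contradict the SAP, and the two would still need to be reconciled.

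**Conclusion.** The rule is wrong as written for one group: patients on a statin at ACS onset and enrolled under amendment 2 or later. Any of them at 70–99 mg/dL would breach I 02 and still count as per-protocol. The number is unknown and may be zero; the range of about 1 to 8 rests wholly on assumed shares, and even its high end moves the PP estimate little.

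The mITT primary analysis, its power and the type I error are unaffected. The multiple-imputation sensitivity analysis uses the randomized population, so it is unaffected too.

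The conclusion rests on I 02 as it stands in amendment 3. The texts of amendments 1 and 2 were not supplied.

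**What to change.** Before database lock, amend the LDL-C bullet in SAP 2.3.1.2 for patients enrolled under amendment 2 or later:

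- **On a statin at ACS onset:** LDL-C at ACS diagnosis ≥100 mg/dL, as I 02 states.
- **Not on a statin at ACS onset:** LDL-C at 2 to 4 weeks after diagnosis not below 70 mg/dL.
- Name the measurement used in each branch instead of referring only to patient selection.

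Reconcile whether the I 02 heading also binds the second branch, given Protocol Sections 4 and 6. Add ≥100 mg/dL at diagnosis to that branch in PP only if it does; otherwise PP could lose patients whom those sections admit. Take the amendment 1 rule from the amendment 1 text. Correct the explanation in SAP 1.6 to match.

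The cost is a few lines of SAP text and one derivation split by stratum. PP may lose a few patients. The sponsor must first confirm that the needed LDL-C values, with their dates, were captured: the protocol records the LDL-C used for selection, but the documents do not establish that both a diagnosis and a 2-to-4-week value are held for patients not on a statin.

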10 STUDY PROCEDURES

For all study site visits except the randomization visit (Visit 1/Week 0), a time frame of 7 days before and after the scheduled study site visit will be allowed. For all study site visits after the randomization visit (Visit 1/Week 0), if a visit date is not kept, the next visit is scheduled according to the original schedule as outlined in [Section 1.2](#).

Evaluation IVUS imaging:

The evaluation IVUS imaging will be performed in the same vessels of the initial IVUS imaging at the ACS diagnosis. The Investigator can schedule the evaluation IVUS imaging within 2 weeks before and after the EOT (Week 36; between Week 34 and Week 38). The detailed procedures of IVUS imaging are described in the specific manual. If the evaluation IVUS study cannot be performed by the EOT visit (Week 36) in patients of the alirocumab arm, Praluent® will be administered at Week 36 after data collection listed in the EOT visit (see [Section 10.1.1.1.5](#)), and the evaluation IVUS imaging can be performed before Week 38, while the effect of alirocumab remains. For patients in the SoC arm, the evaluation IVUS imaging should be performed between Week 34 and Week 36 as in the alirocumab arm. If patients cannot undergo the evaluation IVUS imaging by Week 36, all efforts should be made to perform the evaluation IVUS imaging by Week 38.

Blood sampling:

The blood sampling has to be performed in the morning under fasting conditions, which is defined as an overnight fast no less than 8 hours that consist of no food or liquid intake other than water with exception of to do so otherwise by Investigator/sub-Investigator's medical judgment, throughout the study.

The blood sample will be used to measure lipid parameters [TC, LDL-C, HDL-C, TG, non-HDL-C, Apo B, Apo A-1, Apo B/Apo A-1 ratio, Lp(a)], hematology (red blood cell count, hemoglobin, hematocrit, white blood cell count and differential count, platelet count), blood chemistry, HbA1c, hs-CRP, hepatitis B virus antibody, hepatitis C virus antibody, etc (see also [Section 1.2](#)).

Alcohol consumption within 48 hours and intense physical activities within 24 hours preceding the blood sampling are discouraged.

Note: If a patient is not in fasting conditions, the blood sampling will be postponed and a new appointment will be given the day after (or as close as possible to this date) to the patients with instruction to fast.

Laboratory tests:

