## **2.4 STATISTICAL METHODS**

### **2.4.1 Demographics and baseline characteristics**

Parameters described in [Section 2.1.1](#) will be summarized by treatment group and overall using descriptive statistics.

Continuous data will be summarized using the number of available data, mean, standard deviation (SD), median, minimum, and maximum for each treatment group. First quartile (Q1) and third quartile (Q3) will be also provided for baseline IVUS parameters, lipid parameters, HbA1c, hs-CRP. Categorical and ordinal data will be summarized using the number and percentage of patients in each treatment group.

Unless otherwise specified, parameters will be summarized on the randomized population and mITT population analyzed in the treatment arm to which they were randomized. Similar analyses

will be done on the PP population (respectively safety population) in the treatment arm to which they are actually received if the size of the PP population (respectively safety population) is different (>10%) from the size of the mITT population (respectively randomized population) for any treatment group. In the randomized population and mITT population, parameters will also be summarized within each randomization strata as per the registration center and within each diabetic status at baseline.

All reported patient's medical and surgical history and all ongoing reported patients' these histories at the start of study will be presented by primary SOC and HLT. The tables will be sorted by SOC internationally agreed order and decreasing frequency of HLT based on the overall incidence across treatment groups. In addition all medical history of specific interest will be presented by treatment group.

P-values comparing the 2 treatment groups on demographic characteristics, disease characteristics and other baseline characteristic data will be provided for descriptive purpose, as a screening tool, using the Fisher exact test for categorical data and Wilcoxon rank sum test for continuous data.

No specific description of the safety parameters will be provided at baseline. If relevant, the baseline values will be described along with each safety analysis.

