### **Supportive analyses**

The primary efficacy endpoint will be analyzed on PP population to assess the effect due to major protocol deviation and/or premature discontinuation.

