#### ***Supportive analyses of secondary efficacy endpoints of IVUS parameters***

The secondary efficacy endpoints of IVUS parameters will be analyzed on PP population to assess the effect due of major protocol deviation and/or premature discontinuation. Descriptive summaries of IVUS parameters will be also performed on PP population.

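### The SAP's per-protocol rule asks for IVUS in the culprit vessels, while current protocol criterion I 03 accepts culprit or non-culprit vessels, so the rule read literally excludes compliant patients

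*SAP*

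**What the plan says.** SAP section 2.3.1.2 defines the PP population as the mITT population "excluding patients with any major protocol deviations that have significant impact on the primary study objective". It then itemises those deviations. One item is failure to meet any of four restated inclusion criteria. The third of these restates the angiographic stenosis criterion and adds: "The IVUS imaging should be performed in the culprit vessels with some levels of atherosclerosis/stenosis".

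Protocol criterion I 03, in the synopsis and again in section 7.1, leaves the imaged segment to the physician: it may be any segment considered imageable, "regardless of culprit vessels or not culprit vessels) other than the culprit lesions". Protocol section 10 adds no culprit restriction at follow-up: "The evaluation IVUS imaging will be performed in the same vessels of the initial IVUS imaging at the ACS diagnosis".

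SAP section 1.6 says version 2 was revised, among other reasons, "in order to follow the last amended protocol". That revision edited this same PP list. It made the LDL-C line depend on the protocol amendment, added a minimum vessel length, and removed background-therapy deviations because that therapy is left to the doctor. It records no change to the vessel sentence.

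The PP set is used twice for efficacy. For the primary endpoint: "The primary efficacy endpoint will be analyzed on PP population to assess the effect due to major protocol deviation and/or premature discontinuation". For the rest: "The secondary efficacy endpoints of IVUS parameters will be analyzed on PP population", which includes the key secondary endpoint, PAV.

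**The concern.** A non-culprit patient who meets I 03 has not deviated from the current protocol, yet fails a criterion on the SAP's list. The head definition would keep that patient and the list would remove them. The two readings give different PP sets.

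The PP analysis is there to show how far deviations and early discontinuation move the result. If it also removes compliant patients because of the vessel imaged, it becomes partly a culprit-vessel subgroup analysis. The protocol's rationale (section 4) itself names culprit versus non-culprit target vessel as a possible reason why results differ between IVUS programmes. A gap between the PP and mITT estimates could then not be put down to deviations alone. The PP analyses would also lose precision. In an open-label trial, the choice between two readings should not be left until arm-level results are known.

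**Working it through.** **Text comparison**

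| Point | SAP 2.3.1.2 | Protocol I 03 (synopsis and 7.1) |
|---|---|---|
| Vessel to be imaged | Culprit vessels | Culprit or non-culprit |
| Culprit lesion itself | Not addressed | Not to be the evaluated segment |
| Amendment-specific? | No (the adjacent LDL-C line is) | Current text only; earlier versions not available |
| Consequence for a non-culprit patient | Fails a listed criterion, so out of PP | Eligible, no deviation |

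**The plan's own sample size (SAP 1.3)**

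Inputs: difference 8, SD 15, two-sided 5%, power 90%, 25% non-evaluable.

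- Per arm: 2 × (1.960 + 1.282)² × (15/8)² = 73.9, so 74. The plan uses 75.
- Power at 75 per arm: 90.4% by the normal approximation, 90.1% by the noncentral t. The plan states 90%.
- Randomised: 150 / (1 − 0.25) = 200, as stated.

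The design figures reproduce, and this point does not change them.

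**Loss of precision if the sentence is applied literally**

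The share of non-culprit imaging is not in the documents, so a range is assumed. Start from 75 per arm, keep the arms equal and use SD 15. With n per arm after removal, the 95% half-width is 1.96 × 15 × √(2/n). Relative to no removal, the interval widens by 1/√(1 − share).

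| Assumed non-culprit share | PP total | Half-width (points) | Ratio | Power at a difference of 8 |
|---|---|---|---|---|
| 0% | 150 | 4.80 | 1.00 | 90% |
| 10% | 135 | 5.06 | 1.05 | 87% |
| 20% | 120 | 5.37 | 1.12 | 83% |
| 30% | 105 | 5.74 | 1.20 | 78% |
| 40% | 90 | 6.20 | 1.29 | 72% |
| 50% | 75 | 6.79 | 1.41 | 64% |

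Power is by the normal approximation and only indicates scale, since no formal claim rests on the PP analysis. With t quantiles the half-widths at 150, 135 and 75 patients are 4.84, 5.11 and 6.90.

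**The SAP's own size trigger**

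SAP 2.4.1 calls for separate PP baseline tables "if the size of the PP population (respectively safety population) is different (>10%) from the size of the mITT population" in any treatment group. With 75 per arm, 7/75 = 9.3% does not reach this and 8/75 = 10.7% does. Eight non-culprit patients in one arm are enough on this criterion alone.

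**Bias between arms**

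The baseline image is obtained before randomization and the same vessel is imaged at follow-up. An exclusion based on the vessel is therefore based on a pre-randomization feature and does not by itself unbalance the arms. No shift in the treatment estimate is claimed.

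**The case against.** The best defence is that the sentence is descriptive. It says imaging should be in the culprit vessels and follows the real eligibility test, which is stenosis found within a week of onset. Since the list only itemises major protocol deviations, a patient who satisfies I 03 has none and can be kept. That reading is possible, but the sentence stands inside a criterion whose failure means exclusion, and a programmer deriving the PP flag could fairly apply it.

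The sentence may also have been right under an earlier amendment. The SAP shows that patients were enrolled under amendment 1 and under amendment 2 or later, and those versions are not available here. This stands: earlier versions need checking before the text is changed. It does not rescue the current wording, which applies the rule to everyone.

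The size is also open to challenge. The 10% to 50% range is an assumption. The base of 150 is the evaluable design number, which other PP exclusions would reduce first, and covariate adjustment should shorten the absolute half-widths. All of this is fair. The ratios hold as long as the residual SD and the arm balance are the same before and after removal, whatever the starting number.

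Finally, the PP analyses are supportive and carry no alpha. That limits the weight of the point but does not remove it.

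**Conclusion.** The concern holds. The PP vessel rule contradicts the current protocol and, applied as written, removes patients who complied. It should be corrected, but it does not threaten the main result: the mITT primary analysis, the alpha hierarchy and the sample size are untouched.

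The damage is confined to the supportive PP analyses of the primary and secondary IVUS endpoints. They would no longer reflect deviations alone, and their confidence intervals would be about 5% to 41% wider if 10% to 50% of patients were imaged in a non-culprit vessel. The effect is negligible if that share is near zero. These figures assume SD 15, equal arms and 75 per arm before removal.

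A separate, smaller mismatch in the same list runs the other way. For amendment 2 or later, the SAP applies an LDL-C floor of 70 mg/dL to all patients. In I 02 that floor appears only for the 2-to-4-week value in patients not on a statin at ACS onset, under a heading that requires at least 100 mg/dL at ACS diagnosis. This was not quantified.

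**What to change.** Before database lock:

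1. Check the earlier protocol versions for a culprit-vessel requirement.
2. In SAP 2.3.1.2, replace the culprit-vessel sentence with the I 03 rule: a segment the physician considers imageable, in a culprit or non-culprit vessel, outside the culprit lesion. If an earlier version did require the culprit vessel, add a clause limited to patients enrolled under it, in the form already used for LDL-C.
3. If a culprit-vessel-only analysis is wanted, specify it as a subgroup analysis and not as PP.
4. Separately, reconcile the LDL-C line with I 02 by statin status at ACS onset, and say which measurement counts as the selection value in each branch. SAP 2.1.1 (the named case report page) and the notes to protocol section 1.2 already define the term in part.

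The cost is one sentence for the main point and one line for the LDL-C point. The main point needs no new data: SAP 2.1.1 already plans to summarise the location of both the culprit vessels and the analysed IVUS vessels.
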